Subjects randomized to the investigational group at each site will follow the Study Schedule of Activities table in section 7.4 and will complete the study in 8 weeks. The subjects that are randomized to the waitlist group at each site will complete all study activities as outlined below in table 7.4. After completing the 8 weeks of the standard regimen, the subjects may choose to receive the same treatment as was implemented in the investigational group. No study data will be completed; however, patients opting to use the device will be seen at weeks 9, 12, and 16 for a documented safety check as outlined in section 7.4.

Research team members will provide the subjects with a self-care kit and provide instructions on how to use the kit. All subjects will leave the initial baseline visit with the self-care kit (Appendices D & E) that includes:

- Subject Diary (intervention group only)
- Self-care checklist
- Dates and Times for their upcoming appointments
- Contact information and instructions to call if any questions

6.4 Follow Up Visit(s):

The subject follow up visits will occur at 1 and 4 weeks (± 3 days). The study staff will collect the checklist and review the subject diary with the intervention patients during each visit to ensure that all entries are complete and understood by the study staff. Any corrections must be made by the subject, and initialed and dated by them. At the visit, the subject will undergo the study procedures as outlined in the Study Schedule of Activities in section 7.4.

6.5 Final Visit:

The final study visit will occur at 8 weeks (± 3 days). At this visit, the subject will undergo the study procedures as outlined in the Study Schedule of Activities in section 7.4. The study staff will collect the checklist and review the subject diary with the subject during each visit to ensure that all entries are complete and understood by the study staff. Any corrections must be made by the subject, and initialed and dated by them.

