7.2.2 Laboratory Testing

Women of childbearing potential, defined as premenopausal, intact ovaries and uterus, and not on birth control, will be tested for pregnancy using a self-administrator urine pregnancy test. If the pregnancy test is positive, the subject will be excluded from the study.

7.2.3 Feasibility (Appendix E):

7.2.3.1 Adherence and barriers (Both Groups): Subjects will keep a diary of device use and list barriers to use of device (investigational group). A self-care checklist will be completed each week they are in the study (both groups).

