Self-care Checklist			weekly		
Safety					
Adverse Events- CTCAEV4.0*			√	√	√
Satisfaction					
Pretreatment survey**		√			
Post treatment survey **					√
Swelling/Inflammation					
Internal- Endoscopy/Patterson Scale		√			√
Digital Photography		√	√	√	√
Grading and Staging*	√	√	√	√	√
Cytokines		√			√
Function					
Range of motion-jaw, shoulder, neck		√		√	√
Patient Reported Outcome- Neck Disability Index		√		√	√
Patient Reported Outcome- Voice Handicap Index		√		√	√
Symptoms					
Vanderbilt H and N Symptom Survey		√		√	√
Lymphedema Symptom Intensity and Distress Scale		√		√	√
Quality of Life					
Linear Analog Self- Assessment		√		√	√

*=safety checks at week 9, 12, &16 for wait-list group opting to use the device

**=intervention group only

8.0 Study Device Accountability (Appendix I):

The site must maintain a device accountability log for the Flexitouch®. Completion of this log will ensure that all study devices are properly tracked and accounted for throughout the study from the time they are received by the institution to the time they are returned to the study sponsor or other designated site. Device location, subject ID assigned, date subject returned to site, controller disinfected, and final disposition (e.g., returned to sponsor, garments discarded) of all Flexitouch® controllers, and garments will be documented.

Tactile Medical™ must also maintain device accountability documenting all shipments and returns of study devices by serial number, date, and person completing the log. Storage locations for the study devices and garments will be secure (i.e., locked and away from other devices) with access restricted only to investigators and authorized research personnel. At the conclusion of the treatment period, the subject will return the Flexitouch® controller to the study site. Garments may be retained by the subject or discarded. Site personnel will return all controllers and any unused garments to Tactile Medical™ at the completion of the study.

9.1 Risk Analysis and Adverse Events:

9.2 Risk Analysis: The subjects enrolled in the study are not expected to be at any higher or additional risk than those who undergo in-clinic CDT. There is minimal risk with CDT. These risks may include but are not limited to increased swelling and pain.

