9.3 Anticipated Adverse Events: Adverse events associated with lymphedema may include increased swelling and pain. The severity of all anticipated events will be graded according to the CTCAE.¹⁵ During the endoscopy it is possible that the following adverse events could occur 1) allergic reactions to the anesthesia or decongestant if these are used 2) problems with heart rhythm 3) nosebleed or other bleeding 4) sore throat 5) fainting 6) headache and 7) chipped teeth.

9.4 Adverse Event Reporting: An adverse event includes any complication whose clinical significance is greater than anticipated, or which occurs with a frequency greater than that which is usually seen for this type of treatment. A serious adverse event is defined as an event that: 1) results in death; 2) is life-threatening (places the subject at immediate risk of death from the experience as it occurred); 3) results in a persistent or significant disability/incapacity (substantial disruption of one's ability to carry out normal life functions); 4) results in medical or surgical intervention; 5) results in or prolongs an existing hospitalization (even if the hospitalization is a precautionary measure for observation); 6) is medically unexpected, regardless of severity. Investigators must report all serious adverse events to Tactile Medical™ within 72 hours. Serious and/or unanticipated adverse events will be reported in writing to the appropriate IRB in accordance with their policy, but not later than five (5) days.

10.0 Deviation from Study Plan: Any deviation from this protocol undertaken to protect the life or physical well-being of a subject in an emergency must be reported to Tactile Medical™ and the respective IRB as soon as possible, but in no event later than five (5) working days

after the deviation occurred. Anticipated deviations from the protocol in a non-emergency situation must be pre-approved by Tactile Medical™ via telephone, email, fax or mail. It is preferred that deviations scheduled to be performed in a non-emergency situation not be conducted until authorized by Tactile Medical™. All protocol deviations must be documented. A deviation that may affect the scientific soundness of the study, or the rights, safety or welfare of the subject must also be reported to the reviewing IRB. Protocol deviations may necessitate the discontinuation of the subject or the site from the study.

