12.3 Statistical Analysis Plan

Minimization of Bias: Stratified randomization to the study groups within each study site will be conducted. Given that this is a wait list/control design, blinding is not possible. Each subject will be assigned a study ID number that will be used for identification purposes in the data. The study statistician who will have no contact with any study participants and will conduct all analyses.

Missing Data: Randomly missing item responses within the study survey measures will be handled as specified by the measure developers. Nonrandom missing visit data are informative for this study (i.e., may speak to feasibility) – no imputation will be conducted.

Interim Analysis: Given that this is a feasibility study, no interim analyses will be conducted. The primary reason for early stoppage would be adverse events.

Aims:

Primary Aim: To determine the feasibility of use of the Flexitouch® Head and Neck Garment, specifically a) to evaluate implementation fidelity (adherence) and barriers to implementation fidelity, b) to establish safety, and c) to assess satisfaction.

Secondary Aim: To determine the preliminary efficacy of Flexitouch® Head and Neck Garment compared to a wait-list control for the following outcomes: a) reduction in swelling/inflammation, b) function (range of motion cervical, jaw, and shoulder), c) symptoms, and d) quality of life.

12.4 Statistical Analyses:

Aim 1 (feasibility): Descriptive statistics (percentages) will be used to summarize adherence to the protocol, barriers, adverse effects, and ratings of satisfaction. Comparison of the rates observed within each of the study groups will be compared using likelihood Chi-Square tests however it is expected that $\geq 75\%$ of the total number of participants enrolled in the study as a whole will complete the study. At the end of the study, it is expected that participants in the investigational group will report acceptable levels of satisfaction with the device, as indicated by 80% rating the satisfaction items above neutral.

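### Adverse-effect rates are compared between arms, but only the device arm keeps a diary that staff review at visits, which may prompt extra adverse event reports in that arm

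*Combined protocol and SAP*

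**What the plan says.** **Analysis.** Section 12.4, Aim 1: "Descriptive statistics (percentages) will be used to summarize adherence to the protocol, barriers, adverse effects, and ratings of satisfaction". It continues: "Comparison of the rates observed within each of the study groups will be compared using likelihood Chi-Square tests". Adverse effects are thus among the rates put to a between-group test.

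**Diary.** Section 7.2.3.1: "Subjects will keep a diary of device use and list barriers to use of device (investigational group". Section 6.3 puts the diary in the self-care kit of the intervention group only, and the schedule in 7.4 marks both diary rows the same way. At weeks 1 and 4 (6.4) staff are to "review the subject diary with the intervention patients during each visit to ensure that all entries are complete and understood by the study staff". Section 6.5 repeats the review at week 8 without naming a group. Both groups complete a weekly self-care checklist, which staff collect; no entry-by-entry review of the checklist is described.

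**Adverse events.** Section 7.2.3.2 has safety evaluated with CTCAE v4.0 in both groups. The 7.4 row "Adverse Events- CTCAEV4.0" falls at weeks 1, 4 and 8 and has no intervention-only mark. Section 9.3 states: "Adverse events associated with lymphedema may include increased swelling and pain". Section 12.3 says that blinding is not possible.

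**The concern.** A subject who skips a session because of pain or swelling would naturally write that down as a barrier. Staff then discuss the entry at the visit, and the complaint is also an anticipated adverse event. A wait-list subject with the same complaint has no diary to bring it up. That subject has to recall it over the one, three or four weeks since the last visit, or mention it on a checklist whose content is in an appendix not available here.

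The plan does not say how CTCAE events are elicited, whether this happens before or after the diary review, or whether a complaint first seen in the diary counts as an adverse event. The definition in 9.4 turns on whether a complication is greater than anticipated, which is a judgement made by unblinded staff.

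If the diary does bring out extra reports, an excess on the device could not be told apart from real harm in a study whose primary aim (b) is to establish safety. Nor could the analysis repair it, because the source of each event is not recorded.

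**Working it through.** **The plan's own figure.** The only power statement (12.4) is 80% with 20 completers per group for a 0.9 SD difference, with NDI as the example (20 to 11, SD 10). It reproduces: 0.9 × √(20/2) = 2.846; the normal approximation gives Φ(2.846 − 1.960) = 81.2%, and the noncentral t with 38 df gives 79.2%. It says nothing about adverse events, for which the documents give no expected rate.

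**Inputs for the illustration.** From the documents: 20 per group, likelihood chi-square, two-sided 5%. Assumed: a rate is the share of subjects with at least one event; the true rate is the same in both arms, 30-50%; 70% of subjects with an event are found by visit questioning alone and 85% when a diary is also reviewed.

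**Size of the false excess.** Observed rate = true rate × detection probability, so excess = true rate × detection gap.
- True rate 30%: 0.30 × 0.70 = 21.0% against 0.30 × 0.85 = 25.5%. Excess 4.5 points, or 0.045 × 20 = 0.9 subjects.
- True rate 50%: 0.50 × 0.70 = 35.0% against 0.50 × 0.85 = 42.5%. Excess 7.5 points, or 0.075 × 20 = 1.5 subjects.
- Gaps of 10 to 20 points: from 0.30 × 0.10 = 3 points to 0.50 × 0.20 = 10 points, or 0.6 to 2 subjects of 20.

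**Effect on the test.** All outcomes with 20 per arm were enumerated exactly. Under the 70%/85% assumption the test rejects in 6.5% of trials (21.0% v 25.5%) and 7.6% (35.0% v 42.5%). With both arms at 85% detection the figures are 5.2% and 4.6%.

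A wider range follows, with every event found in the device arm and wait-list detection set relative to that. Entries are the chance of a false rejection.

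| True rate | 100% | 90% | 75% | 50% |
|---|---|---|---|---|
| 20% | 5.5% | 5.9% | 8.0% | 16.5% |
| 30% | 5.3% | 5.8% | 8.6% | 20.8% |
| 50% | 4.3% | 5.3% | 11.5% | 37.5% |

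A mild gap shifts the estimate but hardly changes the test. Only a large shortfall in the wait-list arm would often produce false significance, and the documents give no basis for choosing a column.

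**The case against.** The strongest reply is that the formal assessment is the same in both arms: same instrument, same visits. The complaints most likely to overlap are also measured in both arms by other means. Swelling is covered by grading and photographs at baseline and weeks 1, 4 and 8. Pain is covered by the Neck Disability Index and the symptom survey at baseline and weeks 4 and 8. The diary rows stand under Fidelity in 7.4, not Safety. The study is described as preliminary rather than hypothesis-testing, and the possible bias would overstate device harm, not hide it.

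Most of this stands, and it rules out several stronger readings:
- A reader might infer that device users keep a daily log of problems. The documents describe a record of use and of barriers to use. The seven-day non-use rule in 5.3.3 implies dated use records, not a daily symptom prompt, and the form itself is in an appendix not seen here.
- A reader might infer that events are in fact more fully detected on the device. Given the common CTCAE schedule, this is a risk and not an established fact.
- A reader might infer that this comparison is the only controlled safety evidence. Blood pressure, pulse and staging are safety checks in 12.4 and are scheduled in both arms.

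What the reply does not remove is the gap in procedure. Equal visits do not ensure equal elicitation when one arm's visits also include going through written complaints and nothing fixes the order or the rule. Surveys and gradings are not said to feed the adverse event record.

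**Conclusion.** The point holds as a risk of unequal ascertainment. It does not hold as a demonstrated bias. The one-arm diary, the staff review, the overlap with anticipated events and the between-arm test are all in the documents; the detection rates are not. Under the assumed 15-point gap and equal true rates of 30-50%, the false excess is 4.5-7.5 points, about 1 to 1.5 subjects of 20, and false rejection rises only to 6.5-7.6%. The practical harm is an estimate that is hard to interpret, more than a misleading p-value. The protection is worth having because it is nearly free and has to be in place before data collection. It would not remove reporting differences that arise because subjects and staff know the allocation.

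**What to change.** **6.4, 6.5 and 7.2.3.2.** State that staff ask the same scripted CTCAE questions in both arms at weeks 1, 4 and 8, before the diary is opened. For each event, record whether it was found by that questioning or only through the diary.

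**12.4.** Report all events by arm. Show the between-arm comparison twice: once with all events, and once restricted to events found by the common questioning. List diary-only events separately. The restricted comparison is a sensitivity analysis and should not replace the full one, because dropping diary-only events altogether could remove genuine device events from the comparison.

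**Cost.** A line in the visit procedure, one extra data field and one extra table. No additional visits are needed.

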7.1 Study Procedures

7.2 Data Collection

7.2.1 Vital Signs/Height and Weight:

Vital signs including blood pressure, pulse and weight will be taken at each study visit. Height will be taken only at baseline by the study team. Each measure will be taken twice and averaged.

7.2.2 Laboratory Testing

Women of childbearing potential, defined as premenopausal, intact ovaries and uterus, and not on birth control, will be tested for pregnancy using a self-administrator urine pregnancy test. If the pregnancy test is positive, the subject will be excluded from the study.

7.2.3 Feasibility (Appendix E):

7.2.3.1 Adherence and barriers (Both Groups): Subjects will keep a diary of device use and list barriers to use of device (investigational group). A self-care checklist will be completed each week they are in the study (both groups).

7.2.3.2 Safety (Both Groups) will be evaluated using CTCAE V4.0¹¹

7.2.3.3 Pre and Post treatment Survey (Intervention Group Only): Subjects will complete a pre and post treatment survey. The survey will be administered at the baseline visit and at the end of the intervention.

7.2.4 Swelling/Inflammation (Appendix F):

7.2.4.1 Endoscopy with Modified Patterson Scale: The Patterson Scale evaluates internal edema in the pharynx and larynx. The Modified Patterson Scale, with established face validity, includes anatomical sites that may develop internal edema.¹²

7.2.4.2 Cytokines: The study nurse or phlebotomist will draw blood at baseline and at the 8-week visit. The following inflammatory markers will be assessed: IFN γ TNF- α , TGF- β , IL-1b, and IL-6. MMP-2, MMP-9, and CRP will also be assessed if testing is available.

7.2.4.3 Digital Photography: At the visits outlined in the Study Schedule of Activities table in section 7.4, subjects will have photos taken of their affected areas to evaluate external swelling/inflammation. These photos will be taken according to the standard procedure as outlined in Appendix F.

7.2.4.4 Grading of External Lymphedema: Trained study personnel will complete a physical examination of the head and neck area. Grading will be documented via the Head and Neck Lymphedema and Fibrosis Assessment criteria.¹³

7.2.5 Function (Appendix G):

7.2.5.1 Neck Disability Index (NDI): This 10-item instrument assesses components of daily life that may be affected by neck pain and dysfunction. Items include pain, personal care, lifting, reaching, headache, concentration, work, driving, sleeping, and recreation. Internal consistency of the 10-item scale is adequate ($\alpha = .89 - .92$).^{14,15} Factor analysis identified one dimension. Stability of the instrument also is adequate ($r = .89$). Validity of the NDI was supported by the moderate to strong correlations with self-reported activity improvement following treatment and pain.

7.2.5.2 Voice Handicap Index (VHI): This 30 item instrument taps function, emotion, and physical areas that may be affected by

voice disorders such as those caused by chemo-radiation therapy for HNC.¹⁶ Internal consistency of the 30-item scale is adequate ($r=0.95$).

7.2.5.3 Cervical and Shoulder ROM: These measurements will be taken according to the instructions provided in Appendix G. The measurements will be taken at intervals outlined in the Study Schedule of Activities table (section 7.4).

7.2.5.4 Jaw ROM: The TheraBite Jaw ROM Scale will be used to measure jaw opening. The Trismus grading criteria from the CTCAE v4.0 also will be recorded.¹¹

7.2.6 Symptoms and Quality of Life (Appendix H)

7.2.6.1 Vanderbilt Head and Neck Symptom Survey plus General Symptom Survey version 2.0 (VHNSS v2.0 plus GSS): The VHNSS v2.0 assesses the prevalence and severity of treatment-related symptoms and their functional impact in patients with head and neck cancer.¹⁷ The VHNSS v.2.0 consists of 50-items within 13 domains including nutrition, swallowing, xerostomia, mucositis, excess mucus, speech, hearing, taste change, smell, dental health, mucosal sensitivity, range of motion, and pain. Items are scored on a numeric scale rating the severity of the symptom from 0 (none) to 10 (severe). The VHNSS v.2.0 takes approximately 10 minutes to complete. VHNSS v2.0 plus GSS includes 12 additional items directed at the systemic effects of therapy. The instrument will be completed by the subjects at the intervals outlined in the Study Schedule of Activities table in section 7.4.

7.2.6.2 Lymphedema Symptom Intensity and Distress Survey (L SIDS-Head and Neck): Lymphedema Symptom Intensity and Distress Survey-Head and Neck, assesses the measurement characteristics of a measure of symptom burden for patients with head and neck lymphedema and is a modified versions of the Lymphedema Symptom Intensity and Distress Survey-Arm.¹⁸

7.2.7 Quality of Life: The 5-item Linear Analog Self-Assessment will be used to evaluate quality of life. The scale assesses physical, emotional, spiritual, intellectual, and over-all well-being, on a 0-10 scale. It has been successfully used in cancer populations.¹⁹

7.3 Study Device Application: The garment will be applied initially with the assistance of the study staff. After the study staff has successfully instructed the subject on how to apply the garment, the subject will be asked to apply the garment with limited assistance, complete a treatment session and then remove the garment. After the removal of the garment, the subject will be asked to don and doff the

garment again without assistance. All subjects will be asked to complete one self-administered treatment under the observation of study team members.

7.4 Study Schedule of Activities:

	Screening/ Randomization	Baseline Visit	Follow Up Week 1	Follow Up Week 4	Final Week8
Patient Characteristics					
Medical History		√			
Height		√			
Weight		√	√	√	√
Garment Fitting	√				
Vital Signs (BP, Pulse)*		√	√	√	√
Demographics		√			
Pregnancy Testing*		√		√	√
Fidelity					
Adherence-Diary**			√	√	√
Barriers-Dairy**			√	√	√
Self-care Checklist			weekly		
Safety					
Adverse Events- CTCAEV4.0*			√	√	√
Satisfaction					
Pretreatment survey**		√			
Post treatment survey **					√
Swelling/Inflammation					
Internal- Endoscopy/Patterson Scale		√			√
Digital Photography		√	√	√	√
Grading and Staging*	√	√	√	√	√
Cytokines		√			√
Function					
Range of motion-jaw, shoulder, neck		√		√	√
Patient Reported Outcome- Neck Disability Index		√		√	√
Patient Reported Outcome- Voice Handicap Index		√		√	√
Symptoms					
Vanderbilt H and N Symptom Survey		√		√	√
Lymphedema Symptom Intensity and Distress Scale		√		√	√
Quality of Life					
Linear Analog Self- Assessment		√		√	√

*=safety checks at week 9, 12, &16 for wait-list group opting to use the device

**=intervention group only

8.0 Study Device Accountability (Appendix I):

The site must maintain a device accountability log for the Flexitouch®. Completion of this log will ensure that all study devices are properly tracked and accounted for throughout the study from the time they are received by the institution to the time they are returned to the study sponsor or other designated site. Device location, subject ID assigned, date subject returned to site, controller disinfected, and final disposition (e.g., returned to sponsor, garments discarded) of all Flexitouch® controllers, and garments will be documented.

Tactile Medical™ must also maintain device accountability documenting all shipments and returns of study devices by serial number, date, and person completing the log. Storage locations for the study devices and garments will be secure (i.e., locked and away from other devices) with access restricted only to investigators and authorized research personnel. At the conclusion of the treatment period, the subject will return the Flexitouch® controller to the study site. Garments may be retained by the subject or discarded. Site personnel will return all controllers and any unused garments to Tactile Medical™ at the completion of the study.

9.1 Risk Analysis and Adverse Events:

9.2 Risk Analysis: The subjects enrolled in the study are not expected to be at any higher or additional risk than those who undergo in-clinic CDT. There is minimal risk with CDT. These risks may include but are not limited to increased swelling and pain.

9.3 Anticipated Adverse Events: Adverse events associated with lymphedema may include increased swelling and pain. The severity of all anticipated events will be graded according to the CTCAE.¹⁵ During the endoscopy it is possible that the following adverse events could occur 1) allergic reactions to the anesthesia or decongestant if these are used 2) problems with heart rhythm 3) nosebleed or other bleeding 4) sore throat 5) fainting 6) headache and 7) chipped teeth.

9.4 Adverse Event Reporting: An adverse event includes any complication whose clinical significance is greater than anticipated, or which occurs with a frequency greater than that which is usually seen for this type of treatment. A serious adverse event is defined as an event that: 1) results in death; 2) is life-threatening (places the subject at immediate risk of death from the experience as it occurred); 3) results in a persistent or significant disability/incapacity (substantial disruption of one's ability to carry out normal life functions); 4) results in medical or surgical intervention; 5) results in or prolongs an existing hospitalization (even if the hospitalization is a precautionary measure for observation); 6) is medically unexpected, regardless of severity. Investigators must report all serious adverse events to Tactile Medical™ within 72 hours. Serious and/or unanticipated adverse events will be reported in writing to the appropriate IRB in accordance with their policy, but not later than five (5) days.

10.0 Deviation from Study Plan: Any deviation from this protocol undertaken to protect the life or physical well-being of a subject in an emergency must be reported to Tactile Medical™ and the respective IRB as soon as possible, but in no event later than five (5) working days

after the deviation occurred. Anticipated deviations from the protocol in a non-emergency situation must be pre-approved by Tactile Medical™ via telephone, email, fax or mail. It is preferred that deviations scheduled to be performed in a non-emergency situation not be conducted until authorized by Tactile Medical™. All protocol deviations must be documented. A deviation that may affect the scientific soundness of the study, or the rights, safety or welfare of the subject must also be reported to the reviewing IRB. Protocol deviations may necessitate the discontinuation of the subject or the site from the study.

- 11.1 Data/Safety Monitoring & Quality Assurance Procedures: This study will be conducted in accordance with Good Clinical Practice (GCP) and International Conference on Harmonization (ICH) Guidelines, Code of Federal Regulations (CFR), institutional research policies and procedures and other appropriate regulatory requirements to ensure subject safety and quality of clinical procedures related to the conduct of the clinical trial. The investigators will permit regular monitoring, audits and site inspections by the IRB, the sponsor, government regulatory bodies and any institution compliance and quality assurance groups of all study related documents (e.g. medical records, source documents, regulatory documents, data collection instruments, study data, etc.). The investigator will ensure the capability for inspection of applicable study related facilities. Clinical trial monitoring may be conducted to ensure compliance to this protocol.
- 11.2 Site Qualifications: Tactile Medical™ may conduct onsite visits or telephone qualification (pre-study audit) prior to study initiation to verify adequate resources, staffing and a sufficient subject pool.
- 11.3 Data Collection Procedures: All data storage, transmission and management will be conducted using the Research Electronic Data Capture (REDCap) tool.²⁰ REDCap is a software toolset and workflow methodology for the secure electronic collection and management of research data. REDCap servers are housed in a data center located in a HIPAA-compliant environment at Vanderbilt with nightly backups. All web-based information transmission is encrypted. REDCap was developed specifically around HIPAA Security guidelines. REDCap has been disseminated for local use at more than 940 other academic/non-profit consortium partners in 75 countries. Vanderbilt leads the REDCap Consortium, which currently supports more than 99,000 projects and 128,000 users. The toolset supports research studies with data management reports, data integrity reports for data cleaning and evaluation, and tracking reports for longitudinal studies. In the event REDCap is unavailable or the patients prefers to use hard copy, hard copy data will be double entered into REDCap.

Each study site will have a site coordinator who will be responsible for ensuring the quality of all data collected at that site and ensuring that the data have been entered into the central study database. All data collected via paper will be double entered and verified by site staff. The raw data will be collected on study specific source document worksheets and/or site specific documentation if REDCap is not available, which includes but are not limited to, medical records and site generated source worksheets.

- 11.4 Clinical Site Monitoring: Clinical sites will be monitored for compliance with the clinical protocol, investigator agreement, and applicable regulations. Regular contact will be maintained to ensure:
- Subject safety
 - That clinical site staff is well informed on regulations and sponsor requirements.
 - That the clinical protocol is followed
 - That data is gathered in a complete and timely way
 - That problems with data or data collection are addressed appropriately and in a timely manner
 - That AEs are properly reported in a timely manner

Investigator and Institution will permit trial related monitoring, audits, IRB review, and regulatory inspection(s), providing supervised direct access to medical records, source data and documents as appropriate. Monitoring will be performed by Tactile Medical™ and/or designee.

- 11.5 Reports and Records: Records to be maintained by the investigator in a designated study file include:
- Investigational plan and all amendments
 - Signed Investigator Agreement
 - IRB approval letter, including a copy of the approved consent forms, progress reports, Adverse Event Report
 - IRB roster or Assurance number, if applicable
 - All correspondences relating to the conduct of this study between the site and sponsor, IRBs, and study monitor
 - Curriculum Vitae and professional license for all study personnel, if applicable
 - Site personnel signature and documentation regarding the Investigator's delegation of responsibility
 - Clinical Site Visit log
 - Protocol/device related training records for all applicable study personnel
 - Investigational device inventory information including the date, quantity and serial number of all devices and received identification of all subjects who received treatment, and final disposition of the devices.
 - Screening log
 - Reports (see Table 2)

The following records must be maintained for each subject enrolled:

- Signed and dated informed consent forms
- Completed CRFs, queries and source document worksheets (if applicable)
- Complete medical records including procedure reports, lab reports (if applicable), etc.

Investigators are required to prepare and submit to the sponsor or its designees complete accurate and timely reports on this investigation as required by regulations. The types of reports to be submitted are summarized in Table 2.

Table 2: Investigator Reports

Reports	Submit To	Timeframe
Unanticipated Adverse Device Event	Sponsor and Reviewing IRB	As soon as possible but no later than 10 working days
Withdrawal of IRB Approval	Sponsor	Within 5 working days
Progress	Sponsor and Reviewing IRB	Annually, at a minimum
Final	Sponsor and Reviewing IRB	Within 3 months following the completion or termination of the Investigator's part

Subject study records, correspondence files, all supporting study documentation, and reports must remain on file at the investigational site for a minimum of ten years after the conclusion of this study. All investigators must contact Tactile Medical™ prior to destroying or archiving off-site any records and reports pertaining to this study to ensure that they no longer need to be retained on-site.

Additionally, Tactile Medical™ must be contacted if the Investigator plans to leave the investigational site to ensure that arrangements for a new Investigator or records transfer are made prior to the Investigator's departure.

11.6 Change to Study Plan:

Should changes in the study plan or protocol become necessary in the course of the clinical trial, those specific changes will be discussed and agreed upon by the Sponsor, its acting representative if appropriate, Investigator and appropriate IRB approval obtained before the changes are implemented. All changes must be documented.

